We would also be like to assess the burden and natural history of those oral cancer patients reporting to us who might have taken treatments from outside and had not received any standard oral care due to reasons mentioned in the protocol. We will be comparing their findings separately with our two experimental groups. This will help to highlight the importance of having a standard oral care protocol for all patients of oral cancer. Further it will provide us with information about the status of oral health in patients who have not received any preventive and supportive oral care as a part of their cancer treatment.

The objectives of this study are.

1. To compare the impact of two professional fluoride application regime on DMFT index among patients with oral & oro-pharyngeal cancer.
2. To validate, pilot test, document and standardize institutional oral care protocol for all patients of oral & oro-pharyngeal cancer.

2. Hypothesis

H0: There will be no difference in outcome between two professional fluoride application regimes regarding defined parameters in patients of oral & oro-pharyngeal cancer.

H1: Fluoride application regime with monthly professional application will have better outcome as compared to four monthly application in cancer patients regarding defined parameters.

3. Methods:

Objective 1: To compare the impact of two fluoride application regime on DMFT index among oral cancer patients.

Study design: Randomized controlled trial & observation design

After completion of pilot study, validation of institutional oral care protocol this study will start. The study will be a prospective Randomized controlled trial with parallel groups. Intervention group will be receiving monthly professional fluoride application and control group will be receiving four monthly professional fluoride application. Each group will further be divided in to two subgroups with either gel application or varnish application. The groups will be compared for DMFT index to compare the effectiveness of the fluoride application regime at 4 time points (0,1,6,12 months). The study will be conducted at Cancer research institute, Swami Rama Himalayan University, Dehradun (CRI, SRHU). All new cases of oral cancer receiving treatment will be enrolled.

Inclusion criteria:

1. Patient with histopathological diagnosis of squamous cell carcinoma of oral cavity & oro-pharynx.
2. Patient aged 18 years and above
3. More than 10 teeth in oral cavity
3. Gives consent

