Evaluation: Patients will be evaluated for set parameters at baseline, one month after completion of primary treatment, six month and one year after completion of cancer treatment. There will be no blinding of any kind. The patients will be kept on recall

for longer period to study effect on the oral health parameters but this will not be part of the present study.

Sample size: Present study will be a prospective randomized parallel group study with allocation ratio of 1:1. As there is no previously available data on frequency of fluoride application as proposed by us. We assume that fluoride monthly application will result in 60 % reduction in decay and quarterly application will result in 30 % reduction in decay at end of 1 year observation period. New patients with established diagnosis of oral cancer will be enrolled as per protocol. Sample of 60 patients in each group (intervention and control) is planned at 1% alpha and 90% power 95% confidence interval.

Sample size calculation:

$$n = \{Z_{1-\alpha/2} \sqrt{P_1(1-P_1)} + Z_{1-\beta} \sqrt{P_2(1-P_2)}\}^2 / (P_1-P_2)^2$$

$$n = 54$$

We assume that monthly professional monthly fluoride application with standard oral care protocol will improve oral health and quality of life parameters by 60 % and Four monthly professional fluoride standard oral care protocol will improve oral health and quality of life parameters 30 % at one year after completion of the study. We will be considering taking 20% as attrition rate (20% of 54 = 10.8, rounded to 11);

The final sample size will be 66patients per group. (Subdivided in 33 patients in gel and varnish group)

The annual load of oral cancer reported at CRI SRHU is approximately 200. We will be randomly recruiting 66 cases in both groups. Each group will be further divided into two subgroups to receive either gel or varnish application.

Statistical analysis: The data will be collected and entered in MS excel 2010. Different statistical analysis will be performed using SPSS software version 22. Intention to treat analysis will be used for the analysis of data.

Trial evaluation and follow up:

The data will be evaluated on 6 monthly duration for adherence to set protocol with information to institutional ethical committee board.

Trial stopping rules:

The clinical trial will be stopped for any of the following reasons.

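### DMFT effectiveness is compared at months 0, 1, 6 and 12 with no primary time point, while the trial is sized on one contrast at 1 year: name one baseline-adjusted 12-month test

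*Protocol*

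**What the plan says.** Protocol section 3 (Methods, Objective 1, Study design) sets out the comparison: "The groups will be compared for DMFT index to compare the effectiveness of the fluoride application regime at 4 time points (0,1,6,12 months". What those months mean is fixed in the Evaluation paragraph: "Patients will be evaluated for set parameters at baseline, one month after completion of primary treatment, six month and one year after completion of cancer". Month 0 is thus the baseline visit, and the other three are counted from the end of cancer treatment. No visit is called primary.

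The null hypothesis in section 2 names neither an outcome nor a time: "There will be no difference in outcome between two professional fluoride application regimes regarding defined parameters". H1 is equally general.

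The Sample size paragraph uses one time point only. Its assumption for the monthly arm is stated as "We assume that fluoride monthly application will result in 60 % reduction in decay". For the control arm the corresponding figure is 30%, and the time to which it refers is "at end of 1 year observation period". On error rates the paragraph adds: "Sample of 60 patients in each group (intervention and control) is planned at 1% alpha and 90% power 95% confidence interval". The calculation gives n = 54 per group, raised to 66 for attrition.

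The Statistical analysis paragraph gives the software and the intention-to-treat principle. It does not say whether or how baseline DMFT enters the comparison.

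**The concern.** The statement of how effectiveness will be judged lists four visits on an equal footing, and one of them precedes any possible effect. A difference at month 0 can only reflect chance in the randomisation. At month 1 the two schedules have had little time to diverge, since the introduction describes the monthly schedule as covering the first year after cancer treatment ends. Only the last visit corresponds to the effect for which the trial was sized.

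Two things are at stake. First, with no primary visit and a hypothesis that names none, a significant result at any visit could be reported as support for H1, so the real error rate would exceed the stated one. The trial is also unblinded, which makes it more important to fix the choice in advance. Second, DMFT counts decayed, missing and filled teeth accumulated over life. DMFT at 12 months is therefore baseline DMFT plus whatever was added since. If the later comparison leaves baseline out, variation from before the trial stays in the error term although the measurement that would remove it is already being collected.

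**Working it through.** **1. The plan's own sizing.** Inputs from the Sample size paragraph: P1 = 0.60, P2 = 0.30, 90% power, and a two-sided level (the formula uses Z at 1−α/2). The usual unpooled formula is n = (Zα/2 + Zβ)² × [P1(1−P1) + P2(1−P2)] / (P1−P2)².

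- At 5%: (1.960 + 1.282)² × (0.24 + 0.21) / 0.09 = 52.5, so 53. The pooled-variance version gives 56. The stated 54 lies between them.
- At 1%: (2.576 + 1.282)² × 0.45 / 0.09 = 74.4, so 75. The pooled version gives 80.
- The formula as printed gives 27 at 5% and 38 at 1%.

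So 54 fits two proportions compared once, at 5%. It does not fit the stated 1% alpha with 90% power. That conflict is a separate matter, but because of it both levels are carried below. The calculation contains one contrast at one time, and no DMFT mean, SD or correlation.

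**2. False-positive rate if the visits are tested separately.** Month 0 is left out, since a difference there could not be claimed as an effect. For three independent tests the rate is 1 − (1−α)³: 14.3% at 5% and 3.0% at 1%. Visits on the same patients are correlated, so the true rate is lower. The documents give no correlation. Simulation of three equicorrelated normal test statistics (1,000,000 draws) gives:

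| Assumed correlation between visits | α = 5% | α = 1% |
|---|---|---|
| 0.5 | 12.5% | 2.7% |
| 0.7 | 10.9% | 2.4% |
| 0.8 | 9.8% | 2.2% |
| 0.9 | 8.4% | 1.9% |

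The rate is above nominal throughout.

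**3. Value of the baseline measurement.** With correlation ρ between baseline and 12-month DMFT, adjustment by ANCOVA multiplies the variance of the group comparison, and so the number of patients needed, by 1 − ρ². The documents give no ρ, so a range is shown.

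| Assumed ρ | 1 − ρ² |
|---|---|
| 0.5 | 0.75 |
| 0.7 | 0.51 |
| 0.8 | 0.36 |
| 0.9 | 0.19 |

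**4. What that means for power.** Assume 66 × 0.8 = 52.8, about 53, completers per group and a true difference of 0.3 SD of 12-month DMFT (assumed, as the protocol gives none). Power is Φ(0.3 × √(53/2) / √(1−ρ²) − Z), with Z = 1.960 at 5%.

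- Unadjusted: 0.3 × 5.148 = 1.544, and Φ(1.544 − 1.960) = 0.34.
- ρ = 0.5: Φ(1.544/0.866 − 1.960) = 0.43.
- ρ = 0.7: Φ(1.544/0.714 − 1.960) = 0.58.
- ρ = 0.9: Φ(1.544/0.436 − 1.960) = 0.94.

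At 1% the same four values are 0.15, 0.21, 0.34 and 0.83. These figures show the direction and range of the gain. They do not estimate this trial's power.

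**The case against.** The strongest reply is that the analysis model belongs in the statistical analysis plan, which is not at hand. Covariates and model form are commonly settled there, and the protocol nowhere says that DMFT will be compared unadjusted. It also speaks of a reduction in decay and of impact on DMFT, which fits change from baseline at least as well as levels. The four visits might feed one repeated-measures test rather than separate tests, and the 1-year sizing already shows which visit was meant.

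Much of this stands. Failure to name a covariate model is no fault in the protocol, and the error rates above apply only if the visits are tested separately. What remains is something the protocol states itself: effectiveness is to be compared at four visits including baseline, none has priority, and the hypothesis names no outcome or time. That text conflicts with a sample size built for one year. Even a repeated-measures test would need to say which contrast decides the trial.

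A reader might go further and infer that the plan compares raw DMFT and that earlier disease will swamp the effect. The listing of month 0 hints at levels, because change from baseline is zero there by definition, but it does not show how later visits are analysed. The introduction describes oral health in the population as poor on average. It gives no spread, and the requirement of more than 10 teeth excludes the most depleted mouths.

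**Conclusion.** The concern holds in this form: the stated comparison does not match the basis of the sample size, and no single test is identified as decisive. If the visits are tested separately, three post-baseline tests carry a false-positive rate of 8.4% to 12.5% against 5%, or 1.9% to 2.7% against 1%, for assumed correlations of 0.9 to 0.5. If baseline DMFT were left out at 12 months, the variance would be larger than necessary by a factor that depends on an unknown correlation: modest at 0.5 (25% saved by adjusting), large at 0.9 (81% saved). Randomisation protects against systematic bias, so the harm is lost power and chance imbalance.

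Two larger figures are tempting but not supported.

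- Counting quality of life as co-confirmatory gives six tests and about 20% at 5% (assumed correlations 0.7 between visits and 0.3 between outcomes). However, the introduction names DMFT as the measure on which the trial is evaluated, Objective 1 names DMFT alone, and Objective 2 places quality of life under an observational design. The outcome list does mention quality of life, so the text is mixed, but 20% is its worst reading.
- Assuming a baseline SD of 6, an increment SD of 2 to 3, a difference of 1.5 teeth and 53 per group, power at 5% rises from 0.21–0.23 to 0.73–0.97 on adjustment. Those SDs imply a correlation of 0.89 to 0.95. With the same total SD (6.3 to 6.7) and a correlation of 0.7 to 0.9, adjusted power is 0.36 to 0.80.

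**What to change.** - Name one confirmatory test: DMFT at 12 months after cancer treatment, monthly against the control regimen, adjusted for baseline DMFT and for formulation (gel or varnish).
- Reword H0 and H1 to that outcome, time and contrast.
- Make DMFT at months 1 and 6 and quality of life secondary.
- Report month 0 descriptively, without a between-group test of effectiveness.
- Restate the power for this test, giving the assumed mean difference, SD and baseline-to-12-month correlation with a range, and settle whether alpha is 1% or 5%.

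The sections also label the control interval differently (quarterly in some places, four-monthly in others). Those passages must be reconciled so that the confirmatory contrast is defined.

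The cost is protocol wording and one calculation, with no new data, since baseline DMFT is already collected. The calculation is needed because n = 54 was derived for proportions of 60% and 30% and does not carry over to a baseline-adjusted comparison of DMFT.

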India is both the highest consumer and producer of tobacco in the world and hence contributes to largest number of newly diagnosed cases of oral cancer annually. Indian population also has very poor oral health indicators compared to western population. It has been established as a fact that Tobacco is a common causative agent and risk factor for both poor oral health and oral cancer.² To make matter worse if the population with very poor oral health also has a high incidence of tobacco use, the transition of oral premalignant lesion into cancer occurs at a faster rate. Tezal et al. in their work have reported periodontitis as a risk of developing oral and oropharyngeal cancer.³⁻⁵ These conditions predispose our population to be at a very high risk of oral cancer.

There are various reasons for suboptimal to poor oral care among Indian population, especially those diagnosed with oral cancer.. The main reason is the lack of awareness in oral health and limited government aids for National oral health program.

Quality of life is now becoming the bench mark of treatment evaluation apart from being one of the goals of treatment. Only a disease-free survival isn't considered as a valid success of treatment anymore. Rather a disease free survival with good quality of life is becoming the goal of treatment in these times of patient-centric holistic care. Now in context of cancer care and treatment, 'It is the time of not just adding years in life, but adding life in the years'. Inclusion of oral supportive care increases quality of life in oral cancer patients.⁶⁻⁸

Majority of our patients do not get preventive and supportive oral care form the time of diagnosis of cancer and thereafter as a part of routine protocol in most of

the cancer centers across the country. This is because of lack of integration of dental experts in decision making and as part of the supportive care team of the oncology unit. Very few centers in India have a dental expert as an active part of the oncology cancer care team for supportive and preventive needs of the patients. Patients are also not aware of the oral health supportive care needs during the cancer treatment unless the complications arise after the treatment of cancer.

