Keeping this in consideration we propose use of more stringent professional fluoride application regime of once a month for first one year after oral cancer treatment completion and then at 3 monthly lifelong applications. This will be done along home use of fluoride mouthrinse and fluoride toothpaste lifelong. We would be comparing neutral sodium fluoride gel and varnish use at monthly and three monthly frequency

for first year after radiotherapy. We will be analyzing the clinical benefit of using the proposed fluoride type and frequency for our patients. To best of our knowledge there is no such study conducted before.

There is evidence for both fluoride gel and fluoride varnish as professional application in management of radiation decay in oral cancer patients. Fluoride varnish requires more strict post application routine as compared to gel application. While fluoride gel application has practical issues like gag reflex.²³To best of our knowledge there are no randomized trial on which type of fluoride application is better for oral cancer patients. We aim to also analyze these two forms of professional fluoride applications in our population.

Economics also plays a major role in compliance to oral care for our population. We would also be assessing the economical burden oral care puts on overall expenses in cancer treatment.

The present study will attempt standardization of our oral care module and will test its effectiveness through analysis of outcome in terms of dental health indicators and quality of life among oral cancer patients. This will be done by using the observation design and following patients for a period of one year.

The study will be a prospective randomized controlled trial with two parallel groups. Intervention group will receive the monthly professional fluoride application as part of standard oral care protocol module while the control group will get four monthly professional fluoride application as part of oral care protocol module. Impact on

DMFT index will be the evaluation parameter. This will shed light on need and requirement of fluoride in cancer patients.

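### Month-0 DMFT is listed as an effectiveness comparison and given no role as an adjustment value, so a plain month-12 comparison would lose precision

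*Protocol*

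**What the plan says.** Protocol, section 3 (Methods), Objective 1, Study design: "The groups will be compared for DMFT index to compare the effectiveness of the fluoride application regime at 4 time points". The bracket that follows gives the time points as 0, 1, 6 and 12 months.

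The Evaluation paragraph of the same section identifies the first of these: "Patients will be evaluated for set parameters at baseline, one month after completion of primary treatment", followed by visits six months and one year after cancer treatment ends. Month 0 is therefore baseline.

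The design paragraph of the introductory text says that "DMFT index will be the evaluation parameter". That sentence begins just before a page break and speaks of impact on the index. The PICO list again gives DMFT under the outcome variable.

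The Statistical analysis paragraph adds only intention to treat and "Different statistical analysis will be performed using SPSS software version 22". No increment, change from baseline or baseline covariate is mentioned in the protocol.

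Two further statements bear on how much DMFT will vary at entry. The inclusion criteria ask for "More than 10 teeth in oral cavity", and the introduction says "Indian population also has very poor oral health indicators compared to western population".

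**The concern.** At month 0 the randomised regimens have had no chance to act. A difference between randomised arms at that visit can only be chance, so it says nothing about effectiveness. The useful role of the month-0 value is as a covariate in the later comparison, and the protocol gives it none.

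This matters more for DMFT than for many outcomes. As usually defined, the index counts decayed, missing and filled teeth, so past disease stays in the score and only new disease can respond to the regimen. If month-12 DMFT is compared as it stands, the spread of past disease between patients goes into the standard error, and any chance difference at entry goes, in part or in full, into the estimate. What is at stake is power and the credibility of a single estimate, not its validity on average.

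**Working it through.** **The plan's own figure.** The sample size of 54 per group comes from two proportions, 0.60 and 0.30. With the unpooled formula, two-sided 5% and 90% power, n = (1.960 + 1.282)² × (0.24 + 0.21) / 0.30² = 52.5, so 53. The pooled version gives 56. The stated figure is thus reproduced within 2 at 5%, but not at the 1% alpha also stated (75 unpooled, 80 pooled), nor by the formula as printed (about 38 at 1%, 27 at 5%). On any reading it contains no DMFT mean, SD or correlation, so it cannot show what a DMFT comparison would achieve. I use 54 below as the number analysed per arm.

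**Room for variation at entry.** A patient needs at least 11 teeth. On a 32-tooth count, 32 − 11 = 21 teeth may already be missing; on a 28-tooth count, 28 − 11 = 17. Entrants may therefore have anything from 0 to 21 (or 17) teeth missing, before decayed and filled teeth are counted.

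**Gain from adjustment.** With correlation r between month-0 and month-12 DMFT, covariance adjustment multiplies the variance of the treatment contrast by 1 − r², and the effective size is 54 / (1 − r²). The power columns assume a true difference of 0.3 SD of month-12 DMFT, two-sided 5%, normal approximation. The last column is for change from baseline with equal SDs, where the variance factor is 2(1 − r).

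| r (assumed) | 1 − r² | 54 per arm acts like | Power, plain month-12 | Power, adjusted | Power, change |
|---|---|---|---|---|---|
| 0.5 | 0.75 | 72 | 34% | 44% | 34% |
| 0.7 | 0.51 | 106 | 34% | 59% | 52% |
| 0.8 | 0.36 | 150 | 34% | 74% | 69% |
| 0.9 | 0.19 | 284 | 34% | 95% | 94% |

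**An example in teeth (all values assumed).** Baseline SD 5, SD of the increment 2 and independent of baseline, true difference 1.5 teeth. The SD at month 12 is √(25 + 4) = 5.39 and r = 5 / 5.39 = 0.93. The adjusted SD is 5.39 × √(1 − 25/29) = 2.

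- Two-sided 5%: power 30% plain, 97% adjusted; n per arm for 90% power is 271 against 38.
- Two-sided 1%: power 13% plain, 91% adjusted; n per arm for 90% power is 384 against 53.

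Over baseline SD 4 to 6, increment SD 1.5 to 3 and a difference of 1 to 2 teeth, at 5%, plain power runs from 12% to 68% and adjusted power from 41% to over 99%. These settings imply r of 0.80 to 0.97, so they show the favourable end. The interval from baseline to the last visit spans cancer treatment plus a year, which is a reason to keep r = 0.5 in view.

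**Chance imbalance at entry.** The SE of the month-0 difference is SD × √(2/54) = 0.192 × SD. For an assumed SD of 4 to 7 teeth, the 95% range is ±1.96 × 0.77 = ±1.5 to ±1.96 × 1.35 = ±2.6 teeth. The share that passes into an unadjusted month-12 difference is the baseline slope, r × SD(month 12) / SD(month 0). It is one half at r = 0.5 with equal SDs, and one when the increment is independent of baseline.

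**The case against.** The strongest reply is that the protocol leaves the analysis open. It names software and a population but no test or model, and a statistical analysis plan that is not shown may well adjust for baseline. The bracket of four time points also matches the visit schedule, and a mixed model over those visits would fit the sentence. Other wording leans towards change: impact on the index, and assumed falls in decay of 60% and 30% at one year.

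Much of this stands. A reader might infer that the protocol expressly commits to an unadjusted test of DMFT levels. It does not: a level comparison is the natural reading of comparing groups on an index at listed times, but it is not stated. A reader might also infer that past disease is bound to swamp the regimen effect, that baseline imbalance passes through tooth for tooth, or that the result is biased. The documents give no SD or correlation to support the first. The second needs a baseline slope of one. Randomisation rules out the third. Nor is month 0 shown to precede all fluoride: the introduction describes a professional application before cancer treatment, and its timing relative to the month-0 examination is not given.

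The reply does not dispose of the sentence itself. It lists baseline among the effectiveness comparisons, which is wrong whatever model is used. If change was intended, the sentence does not say so, and change from baseline is zero at month 0 by definition.

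**Conclusion.** The point holds as a correction to one stated sentence. Baseline DMFT should not be listed as an effectiveness comparison, and the protocol should say what it is for. The fault is not that a model is missing.

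The cost of leaving baseline out is precision. It is a factor of about 1.3 in sample size at r = 0.5 (1 / 0.75) and about 5.3 at r = 0.9 (1 / 0.19). That range rests wholly on an assumed correlation; the tooth-unit figures also rest on assumed SDs and a normal approximation. The direction of the gain is secure for any r appreciably above zero, but its size is not known from the documents. The change should be made.

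**What to change.** Replace the comparison sentence under Study design with wording such as: the monthly and control groups will be compared on DMFT at 12 months by analysis of covariance (or an equivalent mixed model) with month-0 DMFT as covariate; month-0 DMFT will be tabulated by group as a baseline characteristic and not compared as an effectiveness result.

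Covariance adjustment is preferable to change from baseline because, with equal SDs, change gains nothing over the plain comparison at r = 0.5, while adjustment gains at every correlation in the table.

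The cost is one sentence in the protocol, carried into any statistical analysis plan. Month-0 DMFT is already to be collected, so no visits, patients or measurements are added.

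### The sample size treats 60% vs 30% reductions in decay as patient proportions, but the planned comparison is of DMFT, a tooth count, so the stated 90% power does not apply to it

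*Protocol*

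**What the plan says.** The Sample size paragraph (Protocol, 3. Methods, Objective 1) assumes that "fluoride monthly application will result in 60 % reduction in decay and quarterly application will result in 30 % reduction in decay" after one year. Below the formula the same percentages are attached to something else: the monthly regime "will improve oral health and quality of life parameters by 60"%, against 30% for the four-monthly regime. The formula has variance terms of the form P(1-P), so the percentages act as P1 and P2, and the result given is n = 54. The error rates are stated as follows: "Sample of 60 patients in each group (intervention and control) is planned at 1% alpha and 90% power 95% confidence interval". Attrition is then added: "We will be considering taking 20% as attrition rate (20% of 54 = 10.8, rounded to 11"). The final figure is 66 per group.

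The outcome is described differently. The introduction says that "DMFT index will be the evaluation parameter". The Study design paragraph says: "The groups will be compared for DMFT index to compare the effectiveness of the fluoride application regime at 4 time points (0,1,6,12 months"). Objective 1 is worded as impact on DMFT, and the PICO list names DMFT beside oral health and quality of life indicators. The Statistical analysis paragraph gives only the software and intention to treat.

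**The concern.** A two-proportion formula needs, for each arm, the share of patients who meet a yes/no criterion. A 60% reduction in decay is a relative change in an amount. Its sampling variance depends on how much patients vary in new decay, and P(1-P) does not describe that. DMFT in its ordinary meaning (the protocol does not spell it out) counts decayed, missing and filled teeth, so the missing input is the SD of DMFT or of its change.

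The planned 66 per group rests wholly on this calculation. If the arms do not differ on DMFT at the end, nobody could say from the protocol whether a worthwhile difference would have been detected.

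**Working it through.** **1. Where 54 comes from.** Inputs from the Sample size paragraph: P1 = 0.60, P2 = 0.30, power 90% (z = 1.282). The test is two-sided because the formula uses 1-α/2.

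- Unpooled, 5%: (1.960 + 1.282)² × (0.24 + 0.21) / 0.30² = 52.5, so 53 per group.
- Pooled, 5%: (1.960 × √(2 × 0.45 × 0.55) + 1.282 × √0.45)² / 0.30² = 55.7, so 56 per group.
- As printed, 5%: (1.960 × √0.24 + 1.282 × √0.21)² / 0.30² = 26.6, so 27; twice 27 is 54.
- At 1% the three versions give 75, 80 and 38.

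The stated 54 is thus a sample size for two proportions at about 5%. With 54 per group, power for that binary comparison is 91% (unpooled) or 89% (pooled) at 5%, and 76% or 72% at 1%.

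**2. What the DMFT comparison needs.** A mean difference and an SD, or a count model with its dispersion. The protocol gives neither, so no single corrected sample size can be computed.

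**3. Illustration as a count (assumed inputs).** Let m be the mean number of newly affected teeth per year without the regimes. Reductions of 60% and 30% leave means of 0.4m and 0.7m, and log(0.7/0.4) = 0.560. Let counts be negative binomial with dispersion k (larger k means less spread). Evaluable number: 66 × 0.8 = 52.8, taken as 53 per arm.

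SE² = (1/53) × (1/(0.7m) + 1/(0.4m) + 2/k); power = Φ(0.560/SE − z), with z = 1.960 at 5% and 2.576 at 1%.

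| m | k | SE | Power, 5% | Power, 1% |
|---|---|---|---|---|
| 1 | 0.5 | 0.387 | 30% | 13% |
| 1 | 1 | 0.334 | 39% | 18% |
| 3 | 1 | 0.250 | 61% | 37% |
| 5 | 1 | 0.229 | 68% | 45% |
| 5 | 2 | 0.184 | 86% | 68% |
| 5 | 3 | 0.166 | 92% | 79% |
| 8 | 2 | 0.168 | 92% | 78% |

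Over m = 1 to 5 and k = 0.5 to 2, power runs from 30% to 86% at 5% and from 13% to 68% at 1%. The last two rows lie outside that range of inputs. If all 66 per arm were evaluable, m = 5 and k = 2 would give 93% at 5%.

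**4. Cross-check on means (assumed SD).** The arms differ by 0.7m − 0.4m = 0.3m. With 54 per group at 5%, power is 97%, 88%, 55% and 34% for an SD of 0.4m, 0.5m, 0.75m and 1.0m.

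**5. Detectable difference.** For 90% power with 53 per arm:

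- 5%: (1.960 + 1.282) × √(2/53) = 0.63 SD
- 1%: (2.576 + 1.282) × √(2/53) = 0.75 SD

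**The case against.** The strongest reply is that nothing here shows the trial to be too small. The values of m and k are not in the protocol, and one step outside the grid power passes 90% at 5%. This stands: a reader might infer from the 30% to 86% range that the trial is underpowered, and the document does not support that.

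Two other tempting arguments also fail. One is that DMFT is cumulative and so cannot fall by 60%. But the assumption is about decay, and the introduction uses caries reduction in the usual sense of less new decay. The other is that no randomised arm goes without professional fluoride, so no reduction can be measured. A between-arm calculation needs only a common assumed reference, and the real gap is that the reference is not stated.

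It can also be said that a responder definition may exist in the operational definitions to which Objective 2 refers, or in an analysis plan not shown here. That is possible, so the point is limited to the protocol as shown. It does not remove the mismatch, because the protocol's objective and stated comparison would still be DMFT.

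**Conclusion.** The point holds as a mismatch between the sample size basis and the stated comparison. The 54 reproduces to within two patients as a two-proportion figure at two-sided 5%, and its 90% power applies only to a comparison of success proportions, which the protocol as shown does not plan. Power for DMFT is unknown. The illustrations run from about 30% to above 90% at 5%, depending wholly on an increment and a spread that the protocol does not give. The randomised comparison itself stays valid; what fails is the justification of its size.

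**What to change.** In the Sample size paragraph, name the between-group comparison of the change in DMFT to 12 months as primary, say from which chart the change is counted, and replace the power statement with the detectable difference at the expected evaluable number. Suggested text: with 53 evaluable patients per arm the trial has 90% power to detect a difference of 0.63 SD (two-sided 5%) or 0.75 SD (two-sided 1%) in the 12-month change in DMFT. Keep only one of the two figures, after the sponsor has reconciled the 1% alpha with the 95% confidence level.

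State the assumed SD in teeth, so that the difference can be read in teeth and judged. The pilot has 10 patients and lasts one month, so it cannot supply a 12-month SD; show a range instead.

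Keeping the formula and defining a yes/no outcome to match it is the weaker route, since the protocol offers no basis for 60% and 30% as rates of any such event.

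Cost: protocol wording and one recalculation. Restating the power needs no extra patients, though it may look less favourable than the present claim.
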